## 5.0 Trial Summary

Full title	A Multi site, placebo controlled, double blind randomised clinical trial evaluating the effectiveness of Szc versus placebo to enable safe optimisation of RAS therapy in patients with diabetic kidney disease.
Short title and/or Acronym	The ORTIZ Study Optimising RASi Therapy with Szc
Trial Design Methodology	Multi site, placebo controlled, double blind randomised clinical trial.
Phase of the Trial	II
Study Duration	18 months, including 14 months recruitment period
Study setting	Multi NHS site UK only
Investigational Medicinal Product(s)	sodium zirconium cyclosilicate
Medical condition or disease under investigation	Diabetic Kidney Disease
Planned Sample Size	116
(Maximum) Treatment duration	12 weeks
Follow up duration	2 weeks
End of Trial definition	The last visit of the last subject

## 8.0 List of Abbreviations / Glossary of Terms

ACE	Angiotensin converting enzyme
ACEi	Angiotensin converting enzyme inhibitor
ADR	Adverse Drug Reaction
AE	Adverse event
ARB	Angiotensin receptor blocker
AZ	AstraZeneca
BMI	Body mass index
BNP	Brain-type natriuretic peptide
BNF	British National Formulary
BP	Blood Pressure
CI	Chief investigator
CKD	Chronic kidney disease
ECG	Electro cardio gram
CRF	Case report form
eCRF	Electronic case report form
eGFR	estimated Glomerular Filtration Rate
HDL	High-density lipoprotein
HRA	Health Research authority
IRAS	Integrated Research Approval System
GI	Gastrointestinal
K	Potassium
KDOQI	Kidney Disease Outcomes Quality Initiative
MHRA	Medicines and Healthcare products Regulatory Agency
MRA	Mineralocorticoid receptor antagonist
NICE	The National Institute for Health and Care Excellence
NIMP	Non investigational medicinal product
OD	Once daily
PI	Principal Investigator
SmPC	Summary of product characteristics
RAS	Renin angiotensin system
RASI	Renin angiotensin system inhibitor
REC	Research Ethics Committee
SAE	Serious adverse event
SAR	Serious adverse reaction
SPC	Summary of product characteristics
SUB-I	Sub investigator
SUSAR	Serious unexpected serious adverse reaction
uACR	Urinary albumin to creatinine ratio
SZC	Sodium zirconium cyclosilicate
WOCBP	Woman of child bearing potential

## 9.0 Introduction

### 9.1 Background

Inhibiting the renin angiotensin (RAS) system has been the cornerstone of therapy for patients with proteinuric CKD for almost 2 decades, to slow the decline in renal function, delay the presence of dialysis and reduce cardiovascular events and death (Parving et al, Brenner et al.). There is evidence in both the cardiac and renal literature that suggests that maximising the dose of RAS therapy leads to improved outcomes over smaller doses of RAS therapy (Khan et al., Rossing et al.)

Indeed, many of the studies on which we base our care use doses which are higher than what the majority of our patients are taking. Thus patients are being systemically undertreated by therapies which have been shown to have robust reno protection. With up to 80% of patients on RASI therapy are not on maximal RASI therapy (Epstein et al, 2015), putting them at risk of a more rapid progression and poorer outcomes and increased healthcare costs (Epstein et al, 2016).

An important reason for this is the presence or fear around hyperkalaemia.

With reports of significantly increased rate of hyperkalaemia seen following increases in prescribing of RASI therapy (Juurlink et al.). These concerns have lead NICE to recommend not starting patients on RASI therapy if their potassium is  $>5\text{mmol/l}$ , and KDOQI guidelines recommending consideration of stopping RASI therapy if serum potassium is  $>5.5\text{mmol/l}$ .

ACE inhibitors and angiotensin receptor blockers are thought to confer long term renal protection through reduction of proteinuria. The reduction in glomerular pressure is a major mechanism leading to a reduction in proteinuria, and hence renal protection, however as a consequence there will also an acute fall in eGFR. Therefore, when starting/up titrating ACEi/ARB it is expected that there will be an acute fall in eGFR, which is expected to be more than compensated for due to the subsequent long term renal protection. Indeed, current NICE guidelines (NICE 2014) do not suggest any alteration in management until the drop in eGFR is  $>25\%$ .

There is a currently huge unmet need to optimise RASI therapy in those patients with hyperkalaemia.

There have been recent advances in novel therapeutics which can lower potassium in patients. One such agent is Sodium zirconium cyclosilicate (Szc).

SZC is a highly selective inorganic cation exchanger designed to entrap potassium in the intestine.

It has been shown to effective in lowering potassium in patients with heart failure, Diabetes, CKD and RASI therapy (Anker et al., Packham et al. and Ash et al., Kosiborod et al.). With around a  $1\text{mmol/l}$  fall in the serum potassium on those treated with SZC, compared to placebo.

In the 5-large clinical trials it appears efficacious, well tolerated and safe.

We propose the following study: the ORTIZ trial will investigate the safety and tolerability of SZC compared to placebo to maximise RASI therapy in patients with moderate to advanced CKD.

## 9.2 Assessment and management of risk

- The known and potential risks and benefits to human subjects.

SZC has been shown to be safe and efficacious in several published clinical trials. However, in this study we will aim to maximise RASI therapy (Irbesartan) using SZC versus placebo.

ADR from SZC: We foresee very little risk in the use of this agent. See SmPC for SZC There is a risk of hypokalaemia in those patients on SZC, however this is rarely at a level with is symptomatic or would lead to a discontinuation of therapy.

ADR from the NIMP irbesartan: (see attached SmPC for Irbesartan)

There are some risks due to the up titration of the RAS therapy, which are well established in our current standards of care.

Hyperkalaemia, in those patients not on SZC. However, we will be monitoring those patients very closely during the study (checking their potassium levels following any dose changes within 2 weeks. With a pre-specified dose escalation/down escalation/stopping protocol to minimise any risk of hyperkalaemia. In addition, all patients will be given advice on a low potassium diet.

Hypotension: as we increase the RASI (Irbesartan) therapy, this can lead to hypotension. However, these agents will only be increased if the BP is  $>120/70$ , so as to minimise the risks, and that the vast majority of the patients will be hypertensive as their background antihypertensive therapy will have been withheld at the start of the study.

- How high is the risk is compared to normal standard practice?

Given the frequency of follow up and the conservative nature of the dosing protocol used, there is only a very small increased risk above our standard clinical procedures.

- Justification for the choice of route of administration, dosage, dosage regimen, and treatment period(s).

Irbesartan is a commonly used RASI: it is being used entirely within its product license and dose.

The dose of SZC is used within its licenced indication and dose.

- Preclinical+ clinical Data –

There have been 5 studies published using this agent, 4 of which in populations similar to our study population, of patients with CKD, heart failure, and on RASI therapy.

- How the risk will be minimised/managed.

The study protocol of up/down titration is used to minimise any episodes of significant hyperkalaemia.

[figure not shown]
*This trial is categorised as:* Type A = No higher than the risk of standard medical care

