### 11.3 Endpoints

#### 11.3.1 Primary Endpoint

- Proportion of patients on Maximum dose (300mg) Irbesartan therapy at the end of 12 weeks compared to placebo

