### 13.8.3 Trial assessments

#### Screening visit

- a. Informed consent
- b. Inclusion/Exclusion criteria
- c. Demographic data
- d. Concomitant Medication
- e. Physical examination
- f. Medical history
- g. ECG with QTc (f) measured
- h. Vital signs (weight/height/BP/pulse)
- i. Laboratory investigations: U+E
- j. Pregnancy test for women of childbearing potential
- k. Stop all antihypertensive medications (unless judged by PI as fulfilling other purpose eg: beta blockers may continue in patients with angina/arrhythmia or as judged by PI as a risk to health to stop all antihypertensives.)

Rescreening: If patient does not meet the inclusion/exclusion criteria patients, but PI feels there is a likelihood of subsequently meeting criteria then the patient may be rescreened (up to a maximum of 3 times)

Within 7-14 days of screening visit

#### Randomisation visit 1

- a. Concomitant Medication
- b. ECG with QTc (f) measured
- c. Confirmation of meeting Inclusion and no Exclusion criteria
- d. Physical examination
- e. Vital signs (weight/BP/Pulse)
- f. Urine ACR
- g. Lab bloods: U+E (including bicarbonate) , FBC, NT pro BNP
- h. Point of care potassium (optional)
- i. Adverse event assessment (AE and SAE)
- j. Randomisation
- k. Study drug dispense and irbesartan dose chosen as per K value\*\*
- l. Patient shown how to take IMP and given first dose in clinic.

Visit 2,3,4,5,6: see protocolised

- a. Concomitant Medication:
- b. IMP accountability\*
- c. Physical examination
- d. Vital signs (weight/BP/Pulse)
- e. ECG with QTc(f) measured
- f. Lab bloods: U+E (including bicarbonate)
- g. Point of care potassium (optional)
- h. Adverse event assessment (AE and SAE)
- i. Up titration assessment using BP/K\*\*/GFR : see protocol figure 13.8.2
- j. Dispense IMP: visit 4 +6 only. At visits 2,3 and 5 unused IMP and nIMP are returned to the patient after accountability.

## Visit 7

- a. Concomitant Medication review
- b. IMP and RASI accountability\*
- c. Physical examination
- d. Vital signs (weight/BP/Pulse)
- e. ECG with QTc (f) measured
- f. Lab bloods: FBC, U+E (including bicarbonate), Pro NT BNP
- g. Point of care potassium (optional)
- h. uACR
- i. Adverse event assessment (AE and SAE)
- j. IMP stopped
- k. Irbesartan stopped and patient returned to their original dose of ACE/ARB

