### 13.8.4 Follow up Procedures

## Visit 8

- a. Concomitant Medication review
- b. Vital signs (weight/BP/Pulse)
- c. Lab bloods: U+E
- d. Physical examination
- e. ECG with QTc(f) measured
- f. Adverse event assessment

BP/pulse to be recorded after resting seated for minimum of 5 minutes: performed in triplicate with the average rate, systolic and diastolic values taken from the second and third readings.

\*IMP accountability includes S2C/placebo and the NIMP: Irbesartan. The patient will be asked to bring back the IMP and Irbesartan to each clinic visit for accountability. The IMP/NIMP will then be given back to the patient, except for visit 4 and 6 where new IMP will be dispensed.

\*\* K value measured using local labs on the day of clinic (an optional point of care potassium can be used to determine the potassium for dispensing purposes if sites use this routinely. Note if there is a discrepancy between point of care potassium and local lab potassium then local lab potassium will be taken as the correct value for protocol decisions)

If K>6 at clinic visit, patient should have repeat K check as an unscheduled visit and management as per local guidelines.

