## 13.9

### IMP withholding criteria

The IMP will be withheld immediately and the patient will receive appropriate medical intervention, but continue in the study if:

- Potassium < 3.5 mmol/L, at any time during the study\*
- Potassium is found to be >6.5 despite not being on ARB any time during the study.
- If an absolute QTc(f) >550ms, or an increase in QTc interval > 60ms from baseline to more than 500ms is reached . All patients meeting the QTc(f)>500ms criterion should immediately have potassium assessed, if not already done within 1 hour of performing the ECG.
- If it is felt to be in the participant's best interest to stop the study treatment
- if the investigator feels that individual adverse events or IMP related side effects compromise the patient's safety or quality of life for example if the investigator feels that hyperkalaemia is a safety risk, then the IMP/or NIMP may be stopped and the patient treated as per local standard of care.
- In addition the patient may be brought up for an unscheduled visit to recheck potassium if felt to be clinically needed as per local practice
- The investigator feels that individual adverse events or new information gained mean that it is not safe to continue the study
- If the patient becomes pregnant.
- If the patient is found to be non-adherent to the study medication (see section 15.19)

If at a subsequent visit(s), and after appropriate management and if the withholding criteria are no longer present the PI may elect to reintroduce the IMP.

\*If a patient develops hypokalaemia (<3.5mmol/l) the IMP will be withheld and the patient will be managed as standard of care. The IMP can only be restarted if hypokalaemia has resolved and the serum potassium has risen to >5mmol/l. If hypokalaemia (serum K <3.5mmol/l) recurs on reintroducing IMP then IMP is permanently withdrawn.

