## 15.15 Dosage modifications

The dose of SZC/placebo and irbesartan will be adjusted at each of the subsequent protocol visits (2, 3, 4, 5 and 6) following the baseline visit, depending on results from the safety assessments (eGFR change from previous test, blood pressure, and potassium level according to the protocolled SZC/placebo and irbesartan dosing schedule. These changes are described in figure in 13.8.2.

The max dose of SZC/placebo will be 10g (2 sachets) OD. The max dose of irbesartan will be 300mg OD.

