11. ASSESSMENT OF OBJECTIVES

Upon successful screening and meeting all eligibility criteria for inclusion into the trial, as specified in the protocol, consenting patients will be randomised to either receive Szc therapy or placebo. Patients will receive trial treatment in accordance with the protocolised management of irbesartan and Szc/placebo, as described in Figure 2.

[figure not shown]
After screening and baseline, patients will be assessed at 1 week, 2 weeks, 4 weeks, 6 weeks, 8 weeks and 12 weeks (end of the trial), as well as a further follow-up assessment at 14 weeks post baseline. The assessment schedule is shown in the Table 1.

Table 1: Schedule of assessment

Schedule of visits	Screening	Visit 1	Visit 2	Visit 3	Visit 4	Visit 5	Visit 6	Visit 7	Follow-up visit	Unscheduled	Early termination visit
Day/Month	Day -14 to -7	Day 0	Day 7 (+/- 2)	Day 14 (+/- 4)	Day 28 (+/- 4)	Day 42 (+/- 4)	Day 56 (+/- 4)	Day 84 (+/- 4)	Day 98 (+/- 4)		
Informed Consent	X										
Eligibility criteria	X	X									
Demographic data	X										
Medical history	X										
Pregnancy test if WOCBP	X										
Concomitant medication	X	X	X	X	X	X	X	X	X	if needed	X
Randomisation		X									
Stop background antihypertensives	X										
First IMP dose at site		X									
Drug accountability (IRB and SZC)			X	X	X	X	X	X		If needed	
IMP and NIMP drug dispense		X			X		X			If needed	
Physical examination	X	X	X	X	X	X	X	X	X	If needed	X
Vital signs	X	X	X	X	X	X	X	X	X	If needed	X
FBC		X						X		If needed	
U+E	X	X	X	X	X	X	X	X	X	If needed	X
Pro NT BNP		X						X			
Optional POC potassium		X	X	X	X	X	X	X			
ECG	X	X	X	X	X	X	X	X	X	If needed	X
Urine collection (uACR)		X						X		If needed	

AE assessment		X	X	X	X	X	X	X	X	X	X
Uptitration of RASI			X	X	X	X	X			If needed	
RASI dose back to baseline								X			X

Figure 2: Protocolised management of irbesartan and SZC/placebo

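### On the visible text, a visit 6 irbesartan change is followed by no scheduled potassium test for 20 to 36 days, against the 2 weeks stated in Protocol 9.2; separately and minor, two starting-dose bands in 15.13 both contain 5.5 mmol/L

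*Protocol*

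**What the plan says.** Protocol 9.2, in its account of the risks of irbesartan up-titration, lists close monitoring as a safeguard against hyperkalaemia: "checking their potassium levels following any dose changes within 2 weeks". The same section then relies on the frequency of follow-up when it judges the added risk to be very small.

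Protocol 15.15 says the doses of SZC/placebo and irbesartan "will be adjusted at each of the subsequent protocol visits (2, 3, 4, 5 and 6", and refers the detail elsewhere: "These changes are described in figure in 13.8.2". Section 13.8.3 lists, for visits 2 to 6, "Up titration assessment using BP/K" together with GFR. Table 1 of the SAP also marks up-titration at visit 6.

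The schedule in Protocol 13.8.2 puts visit 6 at Day 56 and visit 7 at Day 84, each with a window of 4 days either side. U+E is taken at both, with no fixed test between them. SAP 11 gives the same timing: "patients will be assessed at 1 week, 2 weeks, 4 weeks, 6 weeks, 8 weeks and 12 weeks (end of the trial".

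There is an Unscheduled column in which U+E may be done if needed. The visible text gives two routes to it. Section 13.8.4 says "If K>6 at clinic visit, patient should have repeat K check as an unscheduled visit". Section 13.9 says a patient "may be brought up for an unscheduled visit to recheck potassium if felt to be clinically needed".

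On starting doses, Protocol 15.13 gives one regimen for a potassium of 5.1-5.5 mmol/L and another for 5.5-6 mmol/L. Both load with 10 g three times daily for 48 hours. Maintenance is then 5 g once daily in the lower band and 10 g once daily in the upper.

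**The concern.** The 2-week check is offered to readers as a reason why up-titration is safe. The participants are prone to hyperkalaemia: they enter with potassium above 5.0 mmol/L on sub-maximal RASi, or off RASi because of past hyperkalaemia, and are excluded at randomisation only above 6 mmol/L. Because the trial is double blind, the investigator cannot tell which patients lack a potassium binder, so the safeguard has to work for everyone.

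If irbesartan is increased at visit 6 and potassium that day is 6 mmol/L or below, no visible rule requires another test before visit 7. Visit 7 is also when irbesartan stops. The first scheduled test after the change would then come at the end of exposure to the new dose.

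The band overlap is a smaller matter. At exactly 5.5 mmol/L two sites could each follow 15.13 and give different maintenance doses.

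**Working it through.** **Inputs.** The stated limit is 14 days (9.2). Permitted visit days (13.8.2) are: V1 Day 0; V2 5-9; V3 10-18; V4 24-32; V5 38-46; V6 52-60; V7 80-88.

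**Formulas.** Nominal gap = next nominal day − this nominal day. Shortest gap = earliest next day − latest this day. Longest gap = latest next day − earliest this day.

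| Change made at | Next scheduled U+E | Nominal gap | Shortest | Longest |
|---|---|---|---|---|
| V1 | V2 | 7 | 5 − 0 = 5 | 9 − 0 = 9 |
| V2 | V3 | 7 | 10 − 9 = 1 | 18 − 5 = 13 |
| V3 | V4 | 14 | 24 − 18 = 6 | 32 − 10 = 22 |
| V4 | V5 | 14 | 38 − 32 = 6 | 46 − 24 = 22 |
| V5 | V6 | 14 | 52 − 46 = 6 | 60 − 38 = 22 |
| V6 | V7 | 28 | 80 − 60 = 20 | 88 − 52 = 36 |

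**The plan's own figure.** The 2 weeks is reproduced after visits 1 to 5. After visits 1 and 2 the longest gap is 9 and 13 days. After visits 3, 4 and 5 the nominal gap is exactly 14 days. If such a visit falls on day d, day d + 14 always lies inside the next window (for V3, 10 to 18 plus 14 gives 24 to 32, which is the V4 window), so a compliant date always exists.

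**Visit 6.** The shortest gap is 20 days. Of the 9 × 9 = 81 permitted pairs of visit 6 and visit 7 dates, none is within 14 days. The excess over 14 days runs from 20 − 14 = 6 to 36 − 14 = 22, and is 28 − 14 = 14 nominally. The nominal gap is 28/84 = 33% of the treatment period.

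**Timing of a remedy.** A test within 14 days of visit 6 falls by Day 56 + 14 = 70, or by Day 66 to 74 across the visit 6 window. A new visit fixed at Day 70 ± 4 would not be enough: it could fall 66 − 60 = 6 to 74 − 52 = 22 days after visit 6. The limit has to run from the actual date of the change.

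**Band overlap.** Maintenance starts after 2 days of loading and is reassessed at visit 2. The difference is (10 − 5) g/day × (7 − 2) days = 25 g. With visit 2 on Day 5 to 9 it lasts 3 to 7 days, or 15 to 35 g.

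**The case against.** The strongest reply is that the controlling rule may sit where we cannot see it. Section 15.15 refers dose changes to a figure in 13.8.2 that is not shown, as is the corresponding figure in the SAP. A limit on late increases, or a recheck after each change, would naturally belong there. This stands as a condition on the visit 6 point.

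A second reply is that 9.2 does not say the check must be at a scheduled visit, and could itself be read as the trigger for an unscheduled U+E. That is a fair reading, and the plan does contain the means. But the visible rules that send a patient to that column depend on a potassium above 6 mmol/L or on clinical judgement, and a site working from them would have no instruction to test because a dose had changed.

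Third, visit 6 changes are made on that day's blood pressure, potassium and GFR, and the SAP records early closure, so it may be too late to add a test. Both are fair. The first does not replace a test after the change; the second affects which remedy applies.

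Two stronger readings are tempting and are not supported:

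- A reader might infer that visits 3 to 5 also contradict 9.2, since the gap can reach 22 days. The nominal gap is 14 days and a compliant date is always available, so a site can satisfy both the window and 9.2. That calls for a booking reminder only.
- A reader might infer that 9.2 promises a test after every SZC/placebo change. The sentence sits under irbesartan risk and concerns hyperkalaemia in patients not on SZC, so irbesartan changes are its natural scope.

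**Conclusion.** The point holds for irbesartan changes at visit 6, with moderate confidence. The visible schedule does not deliver the 2-week check stated in 9.2: the next scheduled potassium test is 28 days later nominally and 20 to 36 days within windows, so every permitted gap exceeds 14 days, by 6 to 22 days. This assumes that the dosing figure neither bars visit 6 changes nor requires a recheck. If it does either, the point falls.

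The documents do not allow an estimate of how many patients would change dose at visit 6. Nor do they support a claim that the primary endpoint, the sample size or the analysis is affected. This is a mismatch between a stated safety control and the schedule.

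The overlap at 5.5 mmol/L is real and minor. Loading is identical, both maintenance doses are within the 10 g once-daily maximum, and reassessment follows at visit 2. How many patients would read exactly 5.5 is unknown.

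**What to change.** Check the dosing figure first. If it contains no such rule, require a U+E within 14 days of the actual date of any visit 6 irbesartan change, recorded in the existing Unscheduled column (by Day 70 for a nominal visit 6). The cost is one extra blood test per patient changed, at most 116 at the planned sample size.

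If the schedule is to stand, correct 9.2 to say that the interval after visit 6 is about 4 weeks (20 to 36 days). If no patient remains on treatment after the early closure, state that interval in the study report. Either is a wording change.

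Do not remove irbesartan increases at visit 6. That would take away the last of five titration visits before the primary endpoint, "Proportion of patients on Maximum dose (300mg) Irbesartan therapy at the end of 12 weeks compared to placebo".

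For visits 3 to 5, a reminder to book the next visit within 14 days of a change is enough and adds no test.

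Separately, make the 15.13 bands mutually exclusive, for example 5.1-5.5 and 5.6-6.0 mmol/L, with the boundary confirmed by the sponsor's clinicians. This too is wording only.
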